8.3. Safety Assessments

Planned time points for all safety assessments are provided in the SoA (Section [1.3](#)) – where possible, these should be aligned with standard of care.

8.3.1. Physical Examinations

- A complete physical examination will include, at a minimum, assessments of the Skin, Eyes, CV, Respiratory, Gastrointestinal and Neurological systems. Height (screening only) and weight will also be measured and recorded.
- Investigators should pay special attention to clinical signs related to previous serious illnesses.

8.3.2. Vital Signs

- Temperature, pulse rate, and blood pressure will be assessed.
- Blood pressure and pulse measurements will be assessed in the resting state with a completely automated device. Manual techniques will be used only if an automated device is not available.
- Blood pressure and pulse measurements should be preceded by at least 5 minutes of rest for the participant in a quiet setting without distractions (e.g., television, cell phones) and should be taken before blood collection for laboratory tests.

8.3.3. Electrocardiograms (ECGs)

- Twelve-lead ECGs will be obtained at the time points specified in the SoA (see Section 1.3) using an ECG machine, provided by GSK via a designated central laboratory, that automatically calculates the heart rate and measures PR, QRS, QT, and QTc intervals.
- The QTcF formula must be used for *each* individual participant to determine eligibility. This formula may not be changed or substituted once the participant has been enrolled. Refer to Section 7.1.2 for the QTcF formula.
- If an ECG demonstrates a prolonged QT interval, obtain two more ECGs over a brief period, and then use the averaged QTcF values of the three ECGs to determine whether the participant should be screened/ randomised/ discontinued from the study intervention (but not from the study). Refer to Section 5.2 and Section 5.3.2 for exclusion/randomisation exclusion criteria related to ECG assessment and Section 7.1.2 for QTc withdrawal criteria and additional QTc readings that may be necessary.
- ECG measurements will be made after the participant has rested in the supine position for 5 minutes. The ECG should be obtained after the vital signs assessments but before lung function testing followed by other study procedures. Collection shortly after a meal or during sleep should be avoided since QT prolongation can occur at these times.
- Paper ECG traces will be recorded at a standard paper speed of 25 mm/sec and gain of 10 mm/mV, with a lead II rhythm strip. There will be electronic capture and storage of the data by a validated method.
- Paper ECG traces are required to be maintained at the site with other source documents.

8.3.4. Clinical Safety Laboratory Assessments

- See Appendix 2 for the list of clinical laboratory tests to be performed and refer to the SoA (Section 1.3) for the timing and frequency.
- The investigator must review the laboratory report, document this review, and record any clinically significant changes occurring during the study as an AE. The laboratory reports must be filed with the source documents.
- Abnormal laboratory findings associated with the underlying disease are not considered clinically significant, unless judged by the investigator to be more severe than expected for the participant's condition.
- All laboratory tests with values considered clinically significantly abnormal during participation in the study until the Exit Visit (or Follow-up visit/call if applicable) should be repeated until the values return to normal or baseline or are no longer considered significantly abnormal by the investigator or Medical Monitor. If clinically significant values do not return to normal/baseline within a period of time judged reasonable by the investigator, the aetiology should be identified, and the Sponsor notified.

- If laboratory values from non-protocol specified laboratory tests performed at the institution's local laboratory require a change in participant management or are considered clinically significant by the investigator (e.g., SAE or AE), then the results must be recorded.
- All protocol-required laboratory assessments, as defined in Section 10.2, must be conducted in accordance with the laboratory manual and the SoA (Section 1.3).
- To maintain the treatment blind, the site and the central study team will not be sent information on haematology differential (absolute and % values of eosinophils, lymphocytes, basophils, neutrophils, and monocytes) from any visits post-randomisation.

8.3.5. Pregnancy Testing

- Refer to Section 5.1 Inclusion Criteria for pregnancy testing entry criteria.
- A serum pregnancy test should be conducted for all WOCBP at the screening visit (Visit 1) and the Exit visit. In addition, a urine pregnancy test should be performed for all WOCBP prior to randomisation (Visit 2), on a monthly basis at the specified scheduled study visit, and at the Follow-up Visit/call (if applicable) as per the SoA (Section 1.3).
- A final urine pregnancy test should be conducted for all WOCBP, 30 weeks after the last administered dose of study intervention:
 - Participants who enter the OLE study will have a urine pregnancy test prior to receiving the first dose of open-label GSK3511294.
 - Participants who do not enter the OLE study should have a urine pregnancy test at the Follow-up Visit/call (Week 56). A self-reported home urine pregnancy test result is acceptable if the follow-up is conducted as a phone call visit.
 - Participants who withdraw early from the study should have a urine pregnancy test, 4 weeks after the WS Visit (see Section 7.2).
- Additional serum or urine pregnancy tests may be performed, as determined necessary by the investigator or required by local regulation, to establish the absence of pregnancy at any time during the participant's participation in the study.

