4.1.1. Study Phases, Duration and Treatment Arms

At pre-screening, participants will be requested to participate in the study for a maximum of 60 weeks (Visit 0 to the Exit Visit, inclusive) or 64 weeks if not continuing into the OLE Study 212895 (Visit 0 to the Follow-up Visit, inclusive).

During the study, participants will remain on their existing maintenance asthma therapy whilst completing all phases of the study described in Table 1.

Table 1 Study Phases

Phase	Phase Title	Duration	Description
1	Pre-screening (Visit 0)	0-2 weeks	Details about the study and procedures will be explained through the informed consent process. The Pre-screening Visit (Visit 0) can occur on the same day as the Screening Visit (Visit 1) but must be completed prior to initiating any Visit 1 procedures
2	Screening (Visit 1) and Run-in	1-6 weeks	
Participants who meet all the eligibility criteria at Screening (Visit 1) will enter the run-in period for a minimum of 1 week and a maximum of 6 weeks.
 
The run-in is intended to assess the participant's compliance with study-related procedures and continued eligibility for the study as well as to collect baseline eDiary data.
 
Participants who experience an asthma exacerbation during the run-in period should receive treatment for their exacerbation and remain in the run-in period until the investigator considers that the participant has returned to their baseline asthma status for at least one week.
 
The participants that are not eligible to continue in the study at the end of the run-in period will be deemed run-in failures, but may be rescreened after consultation with the Medical Monitor (Section 5.5).

Phase	Phase Title	Duration	Description
3	Study Intervention (Visit 2-Visit 17)	52 weeks	
Participants who meet the randomisation criteria will enter the 52-week treatment period and will be randomised to receive either add-on GSK3511294 (100 mg) or matching placebo in a 2:1 ratio.
 
During the treatment phase, a total of 2 doses of study medication will be administered SC via PFS: at Week 0 (Visit 2) and Week 26 (Visit 10).^a
 
Study visits will occur at Week 0, Week 2, Week 4 and every 4 weeks thereafter with an additional study visit at Week 26 for the administration of the second dose of study intervention. The study intervention period will conclude with the Exit Visit at Week 52 (Visit 17).

Only participants who choose not to enter the OLE study will complete the phase below:			

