7.1.3. Temporary Discontinuation

For this study, a temporary discontinuation refers to a delayed administration of the second dose of study intervention at Week 26.

If a participant becomes infected (parasitic infection) during the study intervention period before receiving the second dose of study intervention and does not respond to anti-helminth treatment, a delayed administration of the study intervention may be considered in consultation with the GSK Medical Monitor.

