7.2. Participant Discontinuation/Withdrawal from the Study

- Participants are strongly encouraged to remain in the study for the entire duration but may prematurely withdraw from the study at any time at his/her own request, at the request of their legally authorised representative (LAR), or may be withdrawn at any time at the discretion of the investigator for safety, behavioural, or compliance reasons. This is expected to be uncommon.
- Participants who prematurely withdraw from the study should attend:
 - a Withdraw from Study (WS) Visit, 26 weeks after the last administered dose of study intervention (at Week 26 or Week 52) **AND**
 - a Follow-up visit/call, 30 weeks after the last administered dose of study intervention for AE/SAE and pregnancy assessments.

Note: this includes any participants who initially discontinue study intervention and remain in the study (Section 7.1) but later decide to withdraw from the study.

- If the participant withdraws consent for disclosure of future information, the Sponsor may retain and continue to use any data collected before such a withdrawal of consent.
- If a participant withdraws from the study, he/she may request destruction of any samples taken and not tested, and the investigator must document this in the site study records.

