- The study investigator is responsible for ensuring that the identification, management, and reporting of AEs and SAEs are completed in accordance with the protocol and applicable regulations. AEs are first reported by participants to the investigator/study team or may be identified by the study team during interactions with the participants via telemedicine encounters. In addition, mobile nurses may identify AEs as well and report them to the investigator for evaluation. Additionally, AEs may be identified from lab reports, imaging or ECG reports, and other records. As determined by the investigator, the appropriate medical intervention, therapeutic intervention, and/or support measures are instituted, as necessary.
- The participant should be informed of the plan and any potential risks associated with the virtual medium and sign a revised Informed Consent Form if required. IRB/Ethics committee should be informed and/or approve of this change in approach and the process documented in study files.
- The revised schedule of study activities is provided in [Table 6](#).

Note: If the investigator wishes to conduct a trial visit at a location that has not been previously assessed by GSK, it is the investigator's responsibility to identify an adequate alternate location and to notify GSK of the alternate location. The investigator should ensure that this alternate location meets ICH GCP requirements, is well-equipped to perform study procedures and covered by an adequate insurance. Furthermore, the investigator should have sufficient oversight to ensure that the staff at the alternate location are trained to perform study procedures. Refer to and follow most recent local guidance and regulations if available or refer to FDA or EMA guidance available at time.

Study Intervention:

- If despite best efforts it is not possible to administer the dose of study intervention as defined in the protocol (see Section 6 Study Intervention and Concomitant Therapy), a maximum dose interval of 28 weeks may be used.
- In-clinic visits are required for administration of the study intervention (Week 0 and Week 26).
- In some cases, trial participants who no longer have access to study intervention or the investigational site may need additional safety monitoring (e.g., on withdrawal of an active investigational treatment).

Data Management/Monitoring:

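### When the second dose is late, the fixed Week 56 contact falls short of the protocol's 30-week interval; separately, the Section 7.2 note can date withdrawal visits in the past

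*Protocol*

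**What the plan says.** Doses are planned "at Week 0 (Visit 2) and Week 26 (Visit 10"). The protocol then times the end of follow-up in two ways.

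**From the last dose.** Section 8.3.5 opens with "A final urine pregnancy test should be conducted for all WOCBP, 30 weeks after the last administered dose of study intervention". Contraception (Section 5.1, criterion 6) and pregnancy collection (Section 8.4.5) also run to 30 weeks from the last dose. Section 7.2 for withdrawn participants, Section 7.3 for those lost to follow-up and Section 6.8 for overdose use 30 weeks as well.

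**From the calendar.** For participants who finish and do not enter the extension, Sections 4.1.2, 8 and 8.3.5 fix the last contact at Week 56. The wording in Section 8.3.5 is "Participants who do not enter the OLE study should have a urine pregnancy test at the Follow-up Visit/call (Week 56"). Table 1 in Section 4.1.1 puts it four weeks after the Exit Visit. Section 8.4.1 ends AE and SAE collection at the Exit Visit or that contact.

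**Late dosing is allowed.** The schedule of activities (Section 1.3) gives a ±7-day visit window. Appendix 11 says "a maximum dose interval of 28 weeks may be used" if the planned dose cannot be given. Section 7.1.3 says that, for a parasitic infection not responding to treatment, "a delayed administration of the study intervention may be considered in consultation with the GSK Medical Monitor"; it states no maximum.

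**Withdrawal.** Section 7.2 asks for "a Withdraw from Study (WS) Visit, 26 weeks after the last administered dose of study intervention (at Week 26 or Week 52") and a follow-up contact at 30 weeks from the last dose. Its note adds that "this includes any participants who initially discontinue study intervention and remain in the study (Section 7.1) but later decide to withdraw from the study". Section 7.1 asks for a withdrawal visit in line with the schedule of activities when such a participant later leaves.

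**The concern.** The calendar rule and the interval rule coincide only if dose 2 is given at Week 26. No section was found that moves the Exit Visit or the Week 56 contact when dose 2 is late. A late-dosed participant who finishes the study would then have the scheduled final pregnancy test before the interval that Section 8.3.5 itself sets. Pregnancy collection would formally still be open, with no scheduled contact to detect an event. The scheduled AE contact would also come sooner after dosing than for a withdrawn participant with the same dose date.

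The second issue is separate. A site following the Section 7.2 note for a one-dose participant who leaves late is told to hold a visit on a date that has gone by. Participants off treatment may continue by phone with a reduced set of assessments (Section 7.1), so for some the withdrawal visit may be the only in-person close-out.

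**Working it through.** **Plan's own figure.** Schedule days: dose 2 on Day 182, Exit on Day 364, follow-up on Day 392.

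- Follow-up minus dose 2: 392 − 182 = 210 days = 30 weeks.
- Exit minus dose 2: 364 − 182 = 182 days = 26 weeks.

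On schedule, the fixed weeks and the intervals agree exactly.

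**Late dose 2.** Weeks of follow-up = follow-up week − week of dose 2, with follow-up at Week 56 ± 1 week.

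| Dose 2 given | Week 55 | Week 56 | Week 57 | Shortfall from 30 at Week 56 |
|---|---|---|---|---|
| Week 26 | 29 | 30 | 31 | 0 |
| Week 27 (visit window) | 28 | 29 | 30 | 1 |
| Week 28 (Appendix 11) | 27 | 28 | 29 | 2 |

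Section 7.1.3 gives no limit, so the following delays are assumptions: dose 2 at Week 30, 32 or 34 gives 26, 24 or 22 weeks to Week 56, short by 4, 6 or 8.

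The Table 1 wording gives the same result unless the Exit Visit itself moves: Week 52 + 4 = Week 56.

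**Same dose date, different exit.** With dose 2 at Week 28, Sections 7.2 and 7.3 place the last contact of a withdrawn or lost participant at Week 28 + 30 = Week 58. A participant who finishes is contacted at Week 56, two weeks earlier.

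**One dose, later withdrawal.** Withdrawal visit due: 0 + 26 = Week 26. Follow-up due: 0 + 30 = Week 30.

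| Leaves at | Withdrawal visit due | Follow-up due |
|---|---|---|
| Week 20 | 6 weeks ahead | 10 weeks ahead |
| Week 27 | 1 week past | 3 weeks ahead |
| Week 40 | 14 weeks past | 10 weeks past |

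Here the interval and the bracketed week in Section 7.2 both give Week 26, so they do not conflict. The past date comes from the dose-based rule. The pregnancy test that Section 8.3.5 places four weeks after the withdrawal visit inherits it: 26 + 4 = Week 30.

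**The case against.** The first part is conditional and small. An on-time dose with follow-up at the early edge of the window already gives 29 weeks, so the protocol tolerates a one-week shortfall. If the Exit Visit is held at Week 53, the Table 1 wording puts follow-up at Week 57, which is 29 weeks after a Week 28 dose. The bracketed Week 56 in Section 8.3.5 can also be read as a gloss on the 30-week sentence. These points limit the size, but they do not remove the contradiction. On the Week 56 wording, no day in the window reaches 30 weeks after a Week 28 dose.

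A reader might infer that finishing participants with a late dose miss a 30-week AE interval set for them. The documents do not support that. The 30-week AE contact is stated only for withdrawn and lost participants and for overdose; Section 8.4.1 ends collection for finishers at Exit or follow-up. What stands is the unequal treatment of participants with the same dose date.

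On the second part, Section 7.1 already asks for a withdrawal visit for this group, Section 8.8 asks for an immunogenicity sample at the final in-clinic visit of early withdrawers, and a one-dose participant attending Week 26 in clinic has most assessments then. The schedule also refers to a footnote c for the withdrawal visit. Its text is not in the copy available for this review, and it may qualify the timing. So a reader should not conclude that these participants necessarily lose their last assessments. What remains is that Section 7.2, taken literally, cannot be carried out and does not sit with Section 7.1.

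**Conclusion.** Both issues stand, with different causes.

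For participants who finish, do not enter the extension and had a late dose 2, the fixed last contact contradicts the 30-week interval for the final pregnancy test, contraception and pregnancy collection. The shortfall at Week 56 is 1 week for a Week 27 dose and 2 weeks for a Week 28 dose, or up to 3 with follow-up held a week early. It has no stated bound under Section 7.1.3. This assumes that the Exit Visit stays at Week 52 and that nothing else in the trial documents moves the contact.

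The past-due withdrawal date holds on the wording of Section 7.2, subject to footnote c. It might be taken as a loss of off-treatment data that the analysis needs, but the SAP does not bear that out: Section 4.1.1 keeps withdrawal-visit assessments out of every statistical analysis, and Section 4.2.3.1 imputes from participants who continued in the study. Nor is the post-dose safety interval shortened for one-dose participants who leave after Week 30, since they have already passed it.

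Power, type I error and the primary analysis are untouched. The documents do not say how many participants either issue would affect.

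**What to change.** Two separate reconciliations are needed; the sponsor decides which timing governs in each.

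1. Bring Protocol Sections 1.3, 4.1.1 (Table 1), 4.1.2, 7.1.3, 8, 8.3.5, 8.4.1 and 8.4.5 and Appendix 11 into line, so that one consistent timing of the last contact and the final pregnancy test applies when dose 2 is late.
2. Reconcile the Section 7.2 note with Section 7.1, Section 8.3.5 and footnote c of the schedule, so that the withdrawal and follow-up dates can be met when the stated interval has already passed at withdrawal.

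The cost is protocol wording and visit-date logic. A few participants' last contact may move by a few weeks. No new procedure is required.

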8.4. Adverse Events (AEs), Serious Adverse Events (SAEs) and Other Safety Reporting

The definitions of adverse events (AE) or serious adverse events (SAEs) can be found in Section 10.3. Asthma exacerbations should not be recorded in the AE section of the eCRF unless they meet the definition of a SAE.

The definitions of device-related safety events, (adverse device effects [ADEs] and serious adverse device effects [SADEs]), can be found in Section 10.7. Device deficiencies are covered in Section 10.7.

AEs will be reported by the participant (or, when appropriate, by a caregiver, surrogate, or the participant's legally authorised representative).

The investigator and any qualified designees are responsible for detecting, documenting, and reporting events that meet the definition of an AE or SAE and remain responsible for following up all AEs that are serious, considered related to the study intervention or the study, or that caused the participant to discontinue the study (see Section 7).

The method of recording, evaluating, and assessing causality of AEs and SAEs and the procedures for completing and transmitting SAE reports are provided in Section 10.3.

8.4.1. Time Period and Frequency for Collecting AE and SAE Information

- All SAEs will be collected from the start of intervention (Visit 2) until the Exit Visit or follow-up visit/call (if applicable) at the time points specified in the SoA (Section 1.3). However, any SAEs assessed as related to study participation (e.g., study intervention, protocol-mandated procedures, invasive tests, or change in existing therapy) or related to a GSK product will be recorded from the time a participant consents to participate in the study.
- All AEs will be collected from the start of intervention until the Exit Visit or the follow-up visit/call (if applicable) at the time points specified in the SoA (Section 1.3).
- Medical occurrences that begin before the start of study intervention but after obtaining informed consent will be recorded as Medical History/Current Medical Conditions (in the eCRF) not as AEs.
- All SAEs will be recorded and reported to the Sponsor or designee immediately and under no circumstance should this exceed 24 hours, as indicated in Appendix 3. The investigator will submit any updated SAE data to GSK within 24 hours of it being available.
- Investigators are not obligated to actively seek information on AEs or SAEs after the conclusion of the study participation. However, if the investigator learns of any SAE, including a death, at any time after a participant has been discharged from the study, and he/she considers the event to be reasonably related to the study intervention or study participation, the investigator must promptly notify GSK.

8.4.2. Method of Detecting AEs and SAEs

Care will be taken not to introduce bias when detecting AE and/or SAE. Open-ended and non-leading verbal questioning of the participant is the preferred method to inquire about AE occurrence.

8.4.3. Follow-up of AEs and SAEs

After the initial AE/SAE report, the investigator is required to proactively follow each participant at subsequent visits/contacts. All SAEs and non-serious AEs of special interest (as defined in Section 8.4.7), will be followed until the event is resolved,

stabilised, otherwise explained, or the participant is lost to follow-up (as defined in Section 7.3). Further information on follow-up procedures is given in [Appendix 3](#).

